While participant monitoring does not occur in real time, any significant physiologic abnormality measured during rehabilitation and transmitted to the server (O₂ saturation less than 80% or heart rate greater than 140 or less than 40 beats per minute) prompts a message to the coach to call the participant to investigate the event. The PI also is alerted within 24 hours by text message if a physiologic abnormality is measured to ensure the appropriate response. In R44HL114162-03 Home-Based Health Management of COPD Patients, the remote rehabilitation and health coaching system has been pilot tested together and found feasible, actionable, and acceptable. After the pilot is completed, a qualitative study will be done to identify areas of deficits to be changed and then adapted for the second phase of the study, a randomized control trial.

Phase 2 (R61): Mayo Clinic Rochester and Jacksonville Fl will participate in this Phase. Phase 2 will take part in year 2 of the study. After the study has been refined in Phase 1, thirty (30) participants (of the planned 150 subjects) will be recruited and randomized to one of two to the home-based PR or referred to conventional PR (standard of care). After the 30 subjects are enrolled, the study staff will review the feasibility, informing the team about accrual and outcome completion rate (questionnaires and activity monitors). This will allow the study team to forecast a complete and informative study for the R33.

The participants randomized to control/conventional care will be offered mileage reimbursement to and from a pulmonary rehab center. The mileage rate used will be the current IRS standard rate (57.5 cents per mile in 2020). The study will pay mileage up to a total of \$500. Study staff will use MapQuest to determine the miles from participants residence to the rehab center. The participants will be asked to sign an Authorization to Release Protected Health Information-Research in order to obtain Pulmonary Rehabilitation Records. Mileage will be paid monthly when possible, or when in receipt of the medical records confirming attendance.

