Phase 3 (R33): Mayo Clinic Rochester and Jacksonville Fl will participate in this Phase. After review of the first 30 participants, the remaining 120 patients with a COPD-related hospitalization (exacerbation or pneumonia) will be randomized at hospital discharge to the home-based PR or usual care (referral to conventional center-based PR). Inclusion, exclusion criteria and recruitment will be identical to the Phase 1 and 2 of the study. Randomization will be completed online through a centralized program Research Electronic Data Capture (REDCap).

The participants randomized to home-based PR will follow the same procedures in the R61 phase, plus any changes suggested by the qualitative study. Any changes will involve a protocol modification and submitted to the IRB for review.

Questionnaires and Activity Monitor: All participants will be asked to complete questionnaires and wear a small activity monitor (Actigraph) at Baseline and Months 3,6 and 12. The participants will be supplied with postage paid envelopes to return the questionnaires and activity monitor.

Questionnaires: Questionnaires include the Medical Research Council (MRC), Chronic Respiratory Questionnaire (CRQ), EuroQol-5D (EQ5D), Patient Health Questionnaire- 9 question (PHQ9), General Anxiety Disorder – 2 question (GAD2), Interpersonal Support Evaluation List (ISEL), Self-Management Ability Scale (SMAS30), Linear Analog Scale Assessment (LASA), Meaning in Life Questionnaire (MIL) and the Working Alliance Inventory (WAI). All questionnaires with the exception of the WAI will be administered at baseline and 3, 6 and 12 Month. The WAI questionnaire will be administered when the participant has completed the Health Coaching Period. For participants randomized to the Intervention arm, the WAI will be administered at 3 months. Participants randomized to the Control/Wait arm will receive the WAI at 6 months. The Charlson Comorbidity Index (CCI) will be included in the baseline questionnaire packet. The CCI will assist in summarizing the enrolled subjects in statistical models.

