For the continuous study outcomes, changes from baseline to three months will be compared between the study arms using two-sample, two-sided t-tests with 5% type I error rates. Changes in QOL, number of steps, and length of stay will be compared between the two treatment sequences using two-sample two-sided t-tests. No adjustments will be made for multiple testing. Means, SDs, medians, ranges, and frequency distributions will be reported and plotted over time by study arm. Linear models will be used to assess the impact of treatment arm on three-month outcomes after adjusting for the corresponding baseline measure and other variables related to the outcome (age, degree of breathlessness at baseline using the mMRC dyspnea, and

FEV1). Repeated measures mixed models will be used to estimate the intervention effect over the 6 months of the study (this will measure trajectory and maintenance of benefits / behavior change). Intent-to-treat analyses will also be performed to determine the sensitivity of the results to dropouts and missing values. In the intent-to-treat analyses, if a month three measure is missing for any reason, it will be described as not changing from baseline. Healthcare utilization (number of ED visits, hospitalizations, and length of stay) between baseline and three months will be treated (analyzed) as both binary (for incidence rates) and continuous (for the number of events). The binary endpoints will all be compared between groups using Fisher's exact test. Logistic regression models will also be fit to look for differences in these outcomes by arm after adjusting for age, mMRC, FEV1, baseline levels of anxiety, depression, and fear, and baseline healthcare utilization, (before starting the study) particularly hospitalizations in the previous year.

Descriptive summaries of the changes between baseline, three, six, and nine months will be used to assess the effect of the home based intervention on the control arm and the residual beneficial effect on the intervention arm. These results will be only descriptive and exploratory. No formal hypothesis testing will be done. All data will be stored in REDCap and analyzed using SAS (Cary, NC).

Per-Protocol Analysis (Dose Response): We will conduct an exploratory analysis to assess the effect of dose of PR sessions on study outcomes. This analysis will control for potential confounders of dose.

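### The hospitalization-or-death endpoint powered at 6 months is not the one named in hypothesis 3d, its alpha is unstated, and wait-list wording conflicts with the parallel design

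*Combined protocol and SAP*

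**What the plan says.** **Hospitalization endpoint.** The Power Statement with its Data Analysis Plan, and Statistical Analysis and Power, list COPD-related hospitalization or death as a secondary endpoint. They assign Fisher's exact test to proportions and claim at least 80% power at 72 per arm for 50% versus 25% at 6 months. Aim 3d defines COPD-related readmission at 1, 3 and 6 months. Hypothesis 3d covers readmissions and ER visits, with its own Fisher test and an adjusted logistic model. A later paragraph of Analyses takes ED visits, hospitalizations and length of stay from baseline to three months.

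**Alpha.** Both power paragraphs open by saying that multiple comparisons have been adjusted for, in the sentence on adherence; the hospitalization sentence follows as a further claim. Analyses sets a 5% two-sided level for continuous outcomes and says that multiple testing will not be adjusted for.

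**Design.** Phase 2 (R61) has patients "recruited and randomized to one of two to the home-based PR or referred to conventional PR (standard of care"; Phase 3 (R33) and the Conventional PR group section describe the same two parallel arms. The Questionnaires section says "The WAI questionnaire will be administered when the participant has completed the Health Coaching Period", which is month 3 for the intervention arm, and then "Participants randomized to the Control/Wait arm will receive the WAI at 6 months". Analyses has changes in quality of life, steps and length of stay "compared between the two treatment sequences using two-sample two-sided t-tests". It also plans "Descriptive summaries of the changes between baseline, three, six, and nine months", to be used "to assess the effect of the home based intervention on the control arm and the residual beneficial effect on the intervention arm". All participants complete questionnaires and "wear a small activity monitor (Actigraph) at Baseline and Months 3,6 and 12".

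**The concern.** A power statement supports a result only if the endpoint, window and alpha behind it are those of the planned test. Here the composite that was powered is not the endpoint named in the hypothesis. The detailed text allows several analyses of hospitalization and none is marked as the main one, so the choice could be made after the data are seen. Reduced readmission is among the findings that the Limitations section hopes will persuade clinicians, regulators and payers.

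The two statements on multiplicity cannot both describe the same test, and the power figure depends on which one applies.

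The wait-list wording raises a separate question about what the later comparisons mean. If controls were offered the home program, the 6-month and one-year results would compare immediate with delayed access. If they are not, the plan schedules a coaching questionnaire and control-arm summaries for something that does not happen.

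**Working it through.** **1. The endpoint, section by section**

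| Section | Outcome | Death included | Window |
|---|---|---|---|
| Both power sections | COPD-related hospitalization or death | yes | 6 months |
| Aim 3d | COPD-related readmission | no | 1, 3 and 6 months, none singled out |
| Hypothesis 3d | Readmissions and ER visits | no | none stated |
| Utilization paragraph of Analyses | ED visits, hospitalizations, length of stay | no | 0 to 3 months |

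Aim 3d loses only the death component. Hypothesis 3d loses death and the window, and adds ER visits. Dropping death lowers the event rate and adding ER visits raises it. The documents give no component rates, so the power for the endpoints actually named cannot be derived from the 50% and 25%.

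**2. The plan's own power figures, then the same figures at an adjusted alpha**

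Inputs from Statistical Analysis and Power: n = 72 per arm; hospitalization or death 50% versus 25%; adherence 26% versus 50%; CRQ difference 0.5 with SD 1.0. Assumptions: two-sided alpha 0.05, and 0.025 as a Bonferroni split over two tests. The documents state neither level for the binary endpoints.

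Exact Fisher power = Σ over x, y of Bin(x; 72, p1) × Bin(y; 72, p2), counting only tables with two-sided Fisher p ≤ alpha.

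Uncorrected normal approximation, with p̄ = (p1 + p2)/2: power = Φ{ [ |p1 − p2|√n − z√(2p̄(1 − p̄)) ] / √(p1(1 − p1) + p2(1 − p2)) }.

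For hospitalization or death:
- |p1 − p2|√n = 0.25 × √72 = 2.121
- √(2 × 0.375 × 0.625) = 0.685
- √(0.25 + 0.1875) = 0.661
- At 0.05 (z = 1.960): (2.121 − 1.342)/0.661 = 1.18, power 88.1%
- At 0.025 (z = 2.241): (2.121 − 1.535)/0.661 = 0.89, power 81.2%

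For CRQ, a t-test with noncentrality 0.5 × √(72/2) = 3.0. The 1,000-step difference with SD 2,000 has the same standardized size.

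| Figure | Planned test, 0.05 | Planned test, 0.025 | Normal approx., 0.05 | Normal approx., 0.025 |
|---|---|---|---|---|
| Hospitalization or death, 50% v 25% | 84.2% | 76.9% | 88.1% | 81.2% |
| Adherence, 26% v 50% | 80.7% | 72.4% | 85.1% | 77.3% |
| CRQ, 0.5 with SD 1.0 | 84.6% | 76.8% | 85.1% | 77.6% |

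At unadjusted 0.05 every printed claim of at least 80% is reproduced. At 0.025 every claim fails under the planned test, and only hospitalization survives under the approximation. The Data Analysis Plan prints 6% instead of 26% for control adherence. At 6% versus 50% the power is about 100% at either level, so that version says nothing about which alpha was used.

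**3. The design wording**

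Coaching lasts twelve weeks. A coaching questionnaire at month 3 for the intervention arm and month 6 for controls would therefore fit a control course starting near month 3. The sequence wording and the control-arm summary fit the same picture. Against it, the arm descriptions give controls a referral, a follow-up call, mileage reimbursement and an activity monitor. No section has a procedure for giving them the home program or coaching. Questionnaires and ActiGraph are scheduled at baseline and months 3, 6 and 12, so the nine-month summary has no such assessment behind it.

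**The case against.** The case on the other side is substantial, and several stronger readings fail against it.

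- **A reader might infer that no 6-month hospitalization test is planned, or that the three-month analysis replaces it.** The documents do not support this. Hypothesis 3d is an explicit test with no three-month limit, its parent aim includes six months, and the power sections assign Fisher's test to proportions. The three-month paragraph uses a different covariate list, which suggests an added analysis. What stands is narrower: death is dropped, and no main window is named.
- **A reader might infer that the 80% claim is false.** It is not, at 0.05. The adjustment clause sits in the adherence sentence and may be a stray phrase; the table in the working favors that. The 0.025 level is an assumption. What stands is that the two sections contradict each other and no alpha is given for this endpoint.
- **A reader might infer that the trial has delayed access, with a measurable loss of power at 6 months.** No section gives a procedure, start time or uptake, and the control-arm summaries are fenced off: "These results will be only descriptive and exploratory. No formal hypothesis testing will be done". Any power figure for a switch would rest wholly on invented inputs. So would one for a three-month window, for which the plan gives no rates and claims no power. I give neither.
- **A reader might see a conflict in the utilization calls** (months 3, 6 and 12, against every three months). Over Aim 3d's six months the schedules agree; only a possible month-9 call differs.

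**Conclusion.** The point holds and should be fixed; it concerns secondary results and the wording of the power statement.

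1. The powered composite, COPD-related hospitalization or death at 6 months, is not the endpoint named in hypothesis 3d. The stated power does not carry over to the endpoints that are named. This rests on the text alone.
2. The two multiplicity statements contradict each other. The printed power fits unadjusted two-sided 0.05 (84.2% for hospitalization or death, 80.7% for adherence at 26% versus 50%). Under a two-test Bonferroni, which is my assumption, exact Fisher power is 76.9% and 72.4%.
3. The wait-list, sequence and nine-month wording conflicts with the parallel design and the assessment schedule. It may be left over from another design, and the documents do not settle whether it is.

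The wait-list wording does not threaten the primary comparison, which scores adherence to each arm's own program, or the month-3 tests, which come before any switch that the questionnaire timing could imply. It matters for interpreting the 6-month hospitalization result, the 6-month mixed model and the one-year cost-effectiveness ratio, and only if controls can in fact receive the home program.

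**What to change.** **Endpoint.** Do one of two things.
- Make hypothesis 3d a single named endpoint that matches the power statement: COPD-related hospitalization or death at 6 months, all randomized patients, by assigned arm, Fisher's exact test. State the population explicitly, because the intention-to-treat sentence under Missing data refers to the repeated-measures method. Label other windows, readmission alone, ED visits, all-cause hospitalization, length of stay and the 0 to 3 month analysis as supporting.
- Or keep Aim 3d's endpoint, name its main window, and restate the power with sourced rates for that endpoint and window.

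**Alpha.** Either delete the multiple-comparisons clause from both power paragraphs and state two-sided 0.05, or keep an adjustment, specify it, restate the power, and remove the contrary sentence in Analyses.

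**Design.** Reconcile the sections on whether controls are offered the home program; that decision belongs to the sponsor. If they are not, delete the wait-list, sequence, control-arm-effect and nine-month wording and the control-arm WAI. If they are, say so and give the procedure, keep all analyses by randomized arm, and describe the 6-month and one-year results as immediate versus delayed access.

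**Cost.** Wording only, with no added patients or visits. The stated power may have to be given as below 80% if an adjusted alpha, or another endpoint or window, is kept.

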We plan to optimize the possibility of patients referred to conventional PR to attend by generating a dialogue about the importance of PR, facilitating the referral and then follow up with a call. This optimization initiative includes targeting the most prevalent problems that explain the current poor utilization of the traditional hospital-based PR after a hospitalization: (1) lack of a referral or strong recommendation from a physician (we plan to do a dedicated referral to the [patient indicating the nearest PR program and contact information including the proper referral order), and (2) inadequate follow-up or facilitation of enrollment after referral (we will communicate with the individuals two weeks after discharge to encourage PR program adherence). Finally, we acknowledge that many patients/caregivers will clearly express being unable to attend conventional PR and realize then that the control arm receive no active intervention. The latter is a significant problem in behavioral interventions that cannot be blinded. *To palliate that problem* and given that the project targets daily physical activity, we will provide every individual in the conventional PR group a Garmin Vivofit (Fig. 3), an activity monitor that has a large display and is easy to use so that they can monitor steps every day. We have ample experience on the use of this monitor in current pour proposal. This is the same monitor that individuals in the Home PR receive for daily use. The study does not cover standard of care treatment. **Home PR group: Proceedings will be as in the pilot study plus refinement (see R61, Phase 1 and 2).**

Recording of calls and qualitative interviews: All health coaching calls and the qualitative interviews will be recorded. The health coaching calls are recorded and the voice file saved on a secure research drive that only study team has access too. The files are saved under the participants subject number and the week of the call. The calls are randomly selected to be reviewed by the PI [name] and the Fidelity Officer, [name]. Dr.'s [name] and [name] will score the health coach using the MITI worksheet (attached, Appendix 1). The voicefiles will be deleted off of the research drive at the end of the study.

Resources:

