Aim 3d: COPD-related hospital readmission (COPD exacerbation or pneumonia as discharge diagnosis) at one month, three months and six months. They will be assessed by the EHR and also by Care Utilization Calls (a safety measure in case individuals are rehospitalized outside the Mayo system). The calls will occur every three months (to avoid recall bias), will use a scripted protocol as in a previous application, and will be conducted by a coordinator blinded to the intervention. Emergency Department (ED) visits and hospitalizations (all cause) will also be recorded.

Aim 4: CE analysis EuroQol Five Dimensions questionnaire

The EuroQol Five Dimensions questionnaire (EQ-5D) is a standardized instrument for measuring generic health status. The health status measured with EQ-5D is used for estimating preference weight for that health status, then, by combining the weight with time, a quality-adjusted life year (QALY) can be computed. QALYs gained its used as an outcome in the cost-utility analysis, which is a type of economic evaluation that compares the benefit and cost of healthcare programs or interventions. EQ-5D is one of the most commonly used generic health status measurements, and its good validity and reliability have been reported in various health conditions. It will be the tool to be used in the proposed cost-effectiveness analysis (CEA).

Secondary Outcomes

Self-Efficacy: The Mastery domain of the CRQ will be used to assess self-efficacy. The CRQ questions assessing self-efficacy are “In the last two weeks, how much of the time did you feel very confident and sure that you could deal with your illness?” and “How often during the last two weeks did you feel you had complete control of your breathing problems?”

Baseline Demographics and comorbidities: Baseline demographics to be collected include age, mMRC, FEV1, highest grade completed in school, marital status, gender, structural and functional social support,³³ race, steroid (prednisone) use in the three months before the study, comorbid conditions (Charlson Comorbidity Index), smoking status, and previous hospitalizations and ED visits.

Analyses

There are three *distinct* quantitative study hypotheses (inform different aspects of the process).

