Assessment of Bias: Potential bias due to loss to follow-up will be assessed using a time to event analysis for the association of patient characteristics with time to dropout; results will be reported and used to evaluate the robustness of the study findings. We will also conduct sensitivity analyses in which missing data for dropouts are imputed under plausible missing-not-at-random assumptions.

Missing data: A common affliction with randomized clinical trial field experiments is noncompliance with both treatment and missing study participation data. To estimate the overall treatment effect for the entire sample, an "intention to treat" analysis will be conducted, using our above likelihood-based analysis method for repeated measures, including data on all subjects who were randomized to the study group. This allows us to use all available data, rather than delete participants with missing values from the analysis of treatment effects.³⁴

Aim 4: Cost-Effectiveness Analysis

This aims to estimate the value of implementing Home PR compared to subjects referred to conventional PR. The CEA, will estimate the ratio of the average change of cost per patient divided by the average change in QALYs per patient for health coaching compared to delivering standard care. QALYs will be based on the EQ-5D-3L³⁵ using a preference-based value set derived from a sample of the US population. QALYs will be calculated by multiplying the utilities by a number of time participants spent in a particular health state. Transitions between health states will be linearly interpolated. The perspective for the CEA is that of the healthcare provider.

For both arms, all resource utilization at the health centers for the one-year period following index hospitalization discharge will be collected. Estimated costs will be standardized using a bottom-up approach. Professional services defined by Current Procedure Terminology code will be valued using national reimbursement amounts from the Medicare fee schedules. Billed charges for hospital services will be valued using department specific cost-to-charge ratios based on the hospital's annual Medicare cost report. All costs will be inflated to a common year using the Gross Domestic Product implicit price deflators.

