Multivariate regression models will be employed to control for differences between study groups. Due to the highly skewed nature of healthcare costs, a generalized linear model incorporating a gamma distribution and log-link function will be used. The cost-effectiveness of the home PR intervention will be determined using the threshold of \$50,000/QALY. The 95% CI of the cost-effectiveness ratio will be calculated using nonparametric bootstrapping.

Healthcare utilization occurring at facilities outside of our network will not be captured. Sensitivity analysis of the cost-effectiveness will be performed based on residency status (local, regional, and distant).

Limitations: We acknowledge that comparing to completed regular PR would be ideal, however, given that the completion rate post-hospitalization is so low, accruing for such a study would be unrealistic. We strongly believe that the proposed design truly represents “a real world” study and the result from it would be applicable to the practicing clinicians and regulatory agencies and payers to further support alternative ways of PR (if our hypothesis is confirmed: increased adherence, decreased readmission and patients’ critical outcomes like daily physical activity and quality of living). We will put a dedicated effort to motivate individual to attend conventional PR if they are randomized to arm.

We will not know if the improvement in adherence is because of the home-based PR or health coaching. However, given that, only 4% complete conventional PR after a hospitalization, a meaningful improvement in adherence would not require much effort from the patients the home-based PR program.

R61 milestones (two years)

Year 1

1. Finalization of the protocol and the informed consent document
2. Development of the manual of operations and case report forms
3. Establishment of a Data and Safety Monitoring Board
4. Institutional Review Board approval of the trial
5. Pilot cohort of 10-15 patients to refine the intervention already developed for outpatients
6. Qualitative study and application of the necessary changes to the proposed Home PR

Year 2

Begin enrollment into the clinical trial to allow for an evaluation by the end of the R61 phase of early enrollment and the probability of completing the trial on time and budget. Target for year two will be to recruit 30 of 150 subjects planned for the whole study.

R33 milestones

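### Aim 4's gamma cost model has no rule for zero captured cost, so a full-likelihood fit may lose randomised patients

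*Combined protocol and SAP*

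**What the plan says.** All of this is in the combined protocol and SAP.

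- **Target.** Aim 4: Cost-Effectiveness Analysis estimates "the ratio of the average change of cost per patient divided by the average change in QALYs per patient". It adds: "The perspective for the CEA is that of the healthcare provider".
- **Cost model.** Because costs are skewed, "a generalized linear model incorporating a gamma distribution and log-link function will be used". No other cost model is named. There is no first part for zero costs, no quasi-likelihood fit and no other rule for zeros.
- **What counts as cost.** For both arms, "all resource utilization at the health centers for the one-year period following index hospitalization discharge will be collected". The index stay therefore falls outside the window. The section also states: "Healthcare utilization occurring at facilities outside of our network will not be captured".
- **Related provision.** A sensitivity analysis by how far away patients live, in three groups. The confidence interval for the ratio comes from a nonparametric bootstrap.
- **Care elsewhere is foreseen.** Under Aim 3d the utilization calls are described as "a safety measure in case individuals are rehospitalized outside the Mayo system". Control patients get a referral "indicating the nearest PR program and contact information including the proper referral order", and that program may lie outside the network.
- **Analysis population.** The Missing data paragraph plans an intention-to-treat analysis of everyone randomised and rejects deleting patients with missing values. It is written for the repeated-measures outcomes and does not mention cost.
- **Software.** SAS is named, but no procedure.

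**The concern.** The gamma distribution covers only values above zero, while the plan's capture rules permit zeros. A patient who gets all care elsewhere for the year has $0 captured cost. So may a patient who dies soon after discharge, and death is part of a planned secondary endpoint. If the fit discards these patients, the cost comparison no longer covers everyone randomised. Mean QALYs could then be averaged over all patients and mean costs only over those with positive cost, so that the two halves of the ratio describe different populations.

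The share of zeros may also differ by arm. The plan does not say whether the tablet, monitors and coaching count as costs. If they do, every home patient has a positive cost and zeros can occur only among controls. Losing them would raise control cost alone and make home PR look cheaper than the captured data show. The result is then judged against $50,000 per QALY.

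**Working it through.** The documents give no mean cost, standard deviation, zero share or power for Aim 4, so there is no stated figure to reproduce. The zero shares and the $20,000 mean below are assumptions. The 75 patients per arm come from Statistical Analysis and Power.

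**1. Can a gamma likelihood use a zero?** The density is proportional to y^(k−1)·exp(−ky/μ), with shape k and mean μ. At y = 0 the log-density is −∞ for k = 2 and +∞ for k = 0.5; it is finite only at k = 1. So in general it cannot.

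**2. Effect on an arm's mean.** Let z be the share with zero captured cost and m the mean among the rest. The mean over all randomised patients is (1 − z)·m. With zeros dropped it is m. The ratio is 1/(1 − z).

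| Assumed z | Patients of 75 | 1/(1 − z) | Simulated ratio, control arm |
|---|---|---|---|
| 5% | 3.75 | 1.053 | 1.054 |
| 10% | 7.5 | 1.111 | 1.112 |
| 20% | 15 | 1.250 | 1.251 |
| 30% | 22.5 | 1.429 | 1.429 |

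The simulation used 100,000 patients per arm, with positive costs drawn from a gamma distribution of shape 0.8 and mean $20,000.

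**3. Zeros in the control arm only.** At z = 20% the algebra gives a control mean of 0.80 × 20,000 = 16,000 against 20,000 at home, a captured difference (home minus control) of +4,000. With zeros dropped both means are 20,000 and the difference is 0. The shift of $4,000 equals 4,000/50,000 = 0.08 QALY at the plan's threshold. Simulated differences:

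| z in controls | All patients | Zeros dropped |
|---|---|---|
| 10% | +1,934 | −74 |
| 20% | +3,790 | −246 |
| 30% | +6,039 | +64 |

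**4. Is the loss built into the model?** No. With a log link and variance proportional to μ², the quasi-likelihood equation is Σ xᵢ(yᵢ − μᵢ)/μᵢ = 0, which is defined at yᵢ = 0. With an arm indicator alone, its solution is the arm mean including zeros. In every simulated setting this fit returned the all-patient captured mean exactly. Where all costs are positive it is also the gamma likelihood's own equation for the coefficients, so the point estimates are the same.

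**5. Captured cost against total cost.** Suppose the zeros stand for care elsewhere that also averages $20,000. At z = 20%, dropping them returns about $20,000, the true total, while keeping them as zeros returns about $16,000. The inflation in step 2 is therefore measured against captured cost only.

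**The case against.** The case on the other side is substantial.

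- **No exclusion is planned.** A reader might infer that zero-cost patients will be dropped. No sentence says so and no SAS procedure is named. Step 4 shows that a fit with the same link and variance function keeps them. This stands: the loss is possible, not planned.
- **Mean cost is not simply overstated.** For a patient treated elsewhere, $0 is uncaptured rather than absent cost, and step 5 shows that dropping can land nearer the true total. This stands too. The inflation is relative to network cost, which fits the stated provider perspective but is not total cost. Likewise, the +$4,000 in step 3 is an artefact of capture if care elsewhere costs the same.
- **Zeros may be few.** Patients are recruited as inpatients, and one network contact in a year removes a zero. Every control patient also receives an activity monitor; if that were costed, exact zeros would disappear. The number is unknown.
- **The log link is not an error.** A reader might infer that the arm coefficient, a cost ratio, will be used as the dollar difference. The plan does not say this, and it defines the numerator as a per-patient average change in cost.
- **The limitation is disclosed.** The residency analysis addresses patients likely to use care elsewhere. It does not say how a zero enters the model.

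What survives is that the only cost model named does not accommodate a value that the plan's own rules allow, and that whether those patients are kept depends on an unstated choice of fit.

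**Conclusion.** The point holds in conditional form. Aim 4 allows $0 captured cost, names a distribution that excludes it and gives no rule. Under a full-likelihood fit the affected patients may be lost, which would run against the all-randomised principle that the plan states for its other outcomes. Mean captured cost in an arm would then be too high by 5%, 11% or 25% at assumed zero shares of 5%, 10% or 20%. If home-program costs are counted and nothing supplied to controls is, the loss would fall on the control arm alone and bias incremental captured cost in favour of home PR.

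The documents do not establish that patients will be dropped, how many zeros there will be, or the size and direction of bias against true total cost. Aim 4 is not the primary endpoint, and the adherence comparison is unaffected. The change is still worth making because it costs almost nothing and leaves the point estimates unchanged if no zeros occur.

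**What to change.** Amend Aim 4 as follows.

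1. Keep the log link and the variance proportional to the squared mean, but fit by quasi-likelihood with robust standard errors. Alternatively, use a two-part model: the probability of any cost times the mean cost among those with cost.
2. State that every randomised patient enters the cost analysis, including those with zero captured cost.
3. Define incremental cost as the difference in average predicted cost with all patients set to each arm in turn, recomputed in each bootstrap replicate.
4. State whether the home program's coaching and devices, and the items supplied to controls, count as cost.
5. Beside the residency analysis, add a sensitivity analysis that treats the cost of patients treated elsewhere as missing rather than zero. Retaining zeros does not by itself solve the capture problem.

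The cost is a few sentences and a small code change, plus some extra analysis for item 5. The core change, items 1 to 3, needs no new data.
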